#### **10.1.9. Publication Policy**

In accordance with the sponsor's publication policy, the results of this study will be submitted for publication by a peer-reviewed journal.

**10.1.10. Investigator Information**

Physicians with a specialty in dermatology will participate as investigators in this clinical study.

**10.1.11. Long-Term Sample Retention**

Sample retention enables use of new technologies, response to regulatory questions, and investigation of variable response that may not be observed until later in the development of lebrikizumab or after lebrikizumab become(s) commercially available.

Sample Type	Custodian	Retention Period After Last Participant Visit*
Long-term storage samples	Sponsor or Designee	15 years
Biomarkers	Sponsor or Designee	N/A
PK	Sponsor or Designee	2 years
Genetics/PD	Sponsor or Designee	15 years
Immunogenicity	Sponsor or Designee	15 years

Abbreviations: N/A = not applicable; PD = pharmacodynamics; PK = pharmacokinetics.

\*Retention periods may differ locally.

## 10.2. Appendix 2: Clinical Laboratory Tests

The tests detailed below will be performed by the central or local laboratory (as applicable) (patient characteristics appropriate reference ranges will be adapted [for example, age, sex]).

- In circumstances where the sponsor approves local laboratory testing in lieu of central laboratory testing (in the table below), the local laboratory must be qualified in accordance with applicable local regulation.
- Protocol-specific requirements for inclusion or exclusion of participants are detailed in Section 5 of the protocol.
- Additional tests may be performed at any time during the study as determined necessary by the investigator or required by local regulations.
- Pregnancy testing is described in the Schedule of Activities (Section 1.3), in Section 8.3.5, and in the table below.

Investigators must document their review of each laboratory safety report.

Laboratory test results that could unblind the study will not be reported to investigative sites or other blinded personnel.

**Clinical Laboratory Tests**

Hematologya,b	Clinical Chemistrya,b
Hemoglobin	Serum Concentrations of:
Hematocrit	Sodium
Erythrocyte count (RBC)	Potassium
Mean cell volume	Chloride
Mean cell hemoglobin	Phosphorus/phosphate
Mean cell hemoglobin concentration	Bicarbonate
Leukocytes (WBC)	Total protein
Platelets	Albumin
Differential WBC [Absolute counts and/or %] of:	Total bilirubin
Neutrophils	Direct bilirubin
Lymphocytes	Alkaline phosphatase (ALP)
Monocytes	Lactic dehydrogenase
Eosinophils	Gamma-glutamyltransferase (GGT)
Basophils	Alanine aminotransferase (ALT)
	Aspartate aminotransferase (AST)
	Blood urea nitrogen (BUN)
	Creatinine
	Uric acid
Urinalysisa	Calcium
Specific gravity	Glucose (random)
pH	Creatine kinase (CK)
Protein	
Glucose	
Ketones	
Blood	
Urine leukocyte esterase	Lipid Panela,b
Bilirubin	High-density lipoprotein (HDL)
Nitrite	Low-density lipoprotein (LDL)
Urobilinogen	Triglycerides
Microscopic examination of sediment c	Total cholesterol
Hormonesa	Pregnancy Test (females only) d (serum a /urine e )
Estradiol (adolescent females only)	
Testosterone (adolescent males only)	
Follicle-stimulating hormone(FSH) f	
Pharmacogeneticsa,g	Serology
	HIV Antibody (HIV Ab) a
	Hepatitis B Core Antibody (HBcAb) a
	Hepatitis B Surface Antigen (HBsAg) a
	Hepatitis B Surface Antibody (HBsAb) a
	Hepatitis B DNA (HBV DNA) a
	Hepatitis C Antibody (HCV Ab) a
	TB Serology h (The QuantiFERON®-TB Gold test or T-SPOT®.TB test or TST)
Other tests	
Pharmacokinetic a,g	
Immunogenicity (anti- ebrikizumab Ab) a,g	
Beta D-glucan	
Thymus and activation-regulated chemokine (TARC) a,g	

Abbreviations: FSH = follicle-stimulating hormone; HIV = human immunodeficiency virus; RBC = red blood cells; WBC = white blood cells.

- a Assayed by Lilly-designated laboratory.
- b Participants should not eat or drink anything except water for 12 hours prior to test. If a participant attends these visits in a nonfasting state, this will not be considered a protocol violation.
- c Test only if dipstick result is abnormal.
- d Local- or investigator-designated laboratory.
- e Urine pregnancy test to be performed only on women of childbearing potential and women with history of tubal ligation. Local testing. Result must be negative before dosing at each dosing visit.
- f For female participants who are >40 to  $\leq$ 55 years of age.
- g Results will not be provided to the investigative sites.
- h The QuantiFERON-TB Gold test may be performed locally or centrally; the T-SPOT must be performed locally.

Selected tests may be obtained in the event of anaphylaxis or systemic allergic/hypersensitivity reactions. The samples should be collected as close as possible to the onset of the event.

After the participant has been stabilized, obtain a sample within 1 to 2 hours of the event; however, samples may be obtained as late as 12 hours after the event, as analytes can remain altered for an extended period of time. Record the time at which the sample was collected.

A follow-up sample should be obtained at the next regularly scheduled visit or after 4 weeks, whichever is later.

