**Study Schedule Protocol J2T-JE-KGAL****Induction Period: Screening Through Week 16**

	Screening	Induction Period										Comments
Visit Number	1	2	3	4	5	6	7	8	9	10		
Weeks from Randomization	–	0	2	4	6	8	10	12	14	16		
Days from Randomization	–	1	14	28	42	56	70	84	98	112		
Visit Tolerance Interval (days)	-7 to -30	–	±3	±3	±3	±3	±3	±3	±3	±3		
Laboratory Testing												
Hematology, clinical chemistry	X	X		X		X		X		X		See Appendix 2 , Clinical Laboratory Tests, for details.
Estradiol or testosterone		X								X		Collect estradiol in adolescent female participants only. Collect testosterone in adolescent male participants only.
Lipids (fasting)		X								X		Participants should not eat or drink anything except water for 12 hours prior before sample collection. If a participant attends these visits in a nonfasting state, this will not be considered a protocol violation.
Pregnancy test	serum	urine		urine		urine		urine		urine		For all women of childbearing potential, a serum pregnancy test (central laboratory) will be performed at Visit 1. Urine pregnancy tests will be performed locally and not captured in eCRF.
FSH	X											For female participants who are >40 to ≤55 years of age.

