**Study Schedule Protocol J2T-JE-KGAL****Maintenance Period: Week 18 to Week 40/Escape Arm**

	Maintenance Period							Comments
	11	12	13	14	15	16	17	
Visit Number	11	12	13	14	15	16	17	
Weeks from Randomization	18	20	24	28	32	36	40	
Days from Randomization	126	140	168	196	224	252	280	
Visit Tolerance Interval (days)	±5	±5	±5	±5	±5	±5	±5	
IWRS entry	X	X	X	X	X	X	X	
Dispense background TCS	X	X	X	X	X	X	X	
Weigh (tube with cap) and record returned background TCS	X	X	X	X	X	X	X	
Dispense IP for home treatment		X	X	X	X	X	X	
IP returned and compliance assessed			X	X	X	X	X	
Administer study intervention	X	X (every 2 weeks)					At Visit 11, participants or their caregiver will administer study intervention under site personnel supervision. Subsequent administration will be administered by participants or their caregiver at home. At Visit 11, for participants in the Escape Arm: 2 injections. All other visits: 1 injection.	
Safety								
Vital signs	X	X	X	X	X	X	X	
Physical examination including height and weight					X			
Concomitant medications/procedures	X	X	X	X	X	X	X	
Adverse events	X	X	X	X	X	X	X	
Investigator Scales								
IGA, EASI	X	X	X	X	X	X	X	
SCORAD	X	X	X	X	X	X	X	

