**Study Schedule Protocol J2T-JE-KGAL****Maintenance Period: Week 18 to Week 40/Escape Arm**

	Maintenance Period							Comments
	11	12	13	14	15	16	17	
Visit Number	11	12	13	14	15	16	17	
Weeks from Randomization	18	20	24	28	32	36	40	
Days from Randomization	126	140	168	196	224	252	280	
Visit Tolerance Interval (days)	±5	±5	±5	±5	±5	±5	±5	
Health Outcomes Measures and Other Questionnaires								
Itch, Sleep-Loss, Skin Pain	X (Will be collected daily via an electronic participant diary)							
POEM (weekly)	X (Will be collected weekly via an electronic participant diary)							Will be collected as eCOA data. Will be completed by the participant prior to any clinical assessments on days of study visits.
DLQI/CDLQI		X	X	X	X	X	X	Will be collected as eCOA data. Will be completed by the participant prior to any clinical assessments on days of study visits.
WPAI-AD				X			X	Will be collected as eCOA data. Will be completed by the participant prior to any clinical assessments on days of study visits.
HADS		X	X	X	X	X	X	Will be collected as eCOA data. Will be completed by the participant prior to any clinical assessments on days of study visits.
C-SSRS 'Since Last Visit'	X	X	X	X	X	X	X	
Self-Harm Supplement Form	X	X	X	X	X	X	X	
Self-Harm Follow-up Form	X	X	X	X	X	X	X	Only required if triggered by the Self-Harm Supplement Form.
Laboratory Testing								
Hematology, clinical chemistry		X		X		X		See Appendix 2 , Clinical Laboratory Tests, for details.
Estradiol or testosterone					X			Collect estradiol in adolescent female participants only. Collect testosterone in adolescent male participants only.
Lipids (fasting)					X			Participants should not eat or drink anything except water for 12 hours prior to sample collection. If a participant attends these visits in a nonfasting state, this will not be considered a protocol violation.
Pregnancy test	urine	urine	urine	urine	urine	urine	urine	Urine pregnancy tests will be performed locally and not captured in the eCRF. If required per investigator judgment, local regulations, and/or institutional guidelines, additional pregnancy testing can occur during the study treatment period.

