**Table 1. Induction Period Dosing Schedule by Treatment Group**

Treatment Assignment in Induction Period (Blinded)	Loading Dose (Baseline and Week 2)	Weeks 4, 8, and 12	Weeks 6, 10, and 14
Lebrikizumab 250 mg Q2W	Baseline: 2 active injections Week 2: 2 active injections	1 active injection	1 active injection
Lebrikizumab 250 mg Q4W	Baseline: 2 active injections Week 2: 2 placebo injections	1 active injection	1 placebo injection
Placebo	Baseline: 2 placebo injections Week 2: 2 placebo injections	1 placebo injection	1 placebo injection

Abbreviations: SC = subcutaneous; Q2W = every 2 weeks; Q4W = every 4 weeks.

Notes: Information provided in this table may change throughout the study. Injections are given SC.

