### **8.2.4. Clinical Safety Laboratory Assessments**

- See [Appendix 2](#) for the list of clinical laboratory tests to be performed and the SoA (Section 1.3) for their timing and frequency. In the opinion of the investigator, if evaluating beta-D-glucan is medically necessary, the investigator may do so at any time during the study, including at screening and during the Safety Follow-Up Period.
- The investigator must review the laboratory report, document this review, and record any clinically relevant changes occurring during the study in the AE section of the CRF. The laboratory reports must be filed with the source documents. Clinically significant abnormal laboratory findings are those which are not associated with the underlying disease, unless judged by the investigator to be more severe than expected for the participant's condition.

- All laboratory tests with values considered clinically significantly abnormal during participation in the study or within 28 days after the last dose of study intervention should be repeated until the values return to normal or baseline or are no longer considered clinically significant by the investigator or medical monitor.
  - If such values do not return to normal/baseline within a period of time judged reasonable by the investigator, the etiology should be identified, and the sponsor notified.
  - All protocol-required laboratory assessments, as defined in [Appendix 2](#), must be conducted in accordance with the laboratory manual and the SoA (Section [1.3](#)).
  - If laboratory values from non-protocol-specified laboratory assessments performed at the institution's local laboratory require a change in participant management or are considered clinically significant by the investigator (for example, SAE or AE or dose modification), then the results must be recorded in the CRF.

Laboratory tests will be analyzed using a central laboratory and will be transferred to the clinical database.

In cases where required blood samples cannot be collected due to blood volume limitation relative to participant size/age, the investigator must consult with Lilly-designated medical personnel to determine which samples to collect. This will not be considered a protocol violation but will need to be documented in the medical record.

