6.5. Appendix 5: Treatment Compliance

Treatment compliance with investigational product will be summarized for participants who have at least one dose for the Safety Population in the Induction Period and for the MPP during the Maintenance Period. Treatment compliance for each participant will be calculated as:

$$\text{Treatment compliance (\%)} = 100 \times \frac{\text{Total number of injections administered}}{\text{Total number of injections expected}}$$

- The number of injections expected can be derived from the study drug dispense dataset.

- The total number of injections administered will be based on the response to the question “Was dose administered?” on the *Exposure as Collected* eCRF page.

The number of injections expected at each visit and total number of injections up to each visit during the Induction Period are as follows:

Visit	W0	W2	W4	W6	W8	W10	W12	W14 ^a
# injections at each visit	2	2	1	1	1	1	1	1
Total # injections up to each visit	2	4	5	6	7	8	9	10

Abbreviation: W = week.

^a Last injection during the Induction Period occurs on Week 14.

The number of injections expected at each visit and total number of injections up to each visit during the Maintenance Period are as follows:

Timepoint	W16	W18	W20	W22	W24	W26	W28	W30	W32	W34
Visit	W16	W18	W20		W24		W28		W32	
# injections at each visit	2	2	1	1	1	1	1	1	1	1
Total # injections up to each visit	2	4	5	6	7	8	9	10	11	12

Abbreviation: W = week.

Timepoint	W36	W38	W40	W42	W44	W46	W48	W50	W52	W54
Visit	W36		W40		W44		W48		W52	
# injections at each visit	1	1	1	1	1	1	1	1	1	1
Total # injections up to each visit	13	14	15	16	17	18	19	20	21	22

Abbreviation: W = week.

Timepoint	W56	W58	W60	W62	W64	W66 ^a	W68
Visit	W56		W60		W64		W68
# injections at each visit	1	1	1	1	1	1	0
Total # injections up to each visit	23	24	25	26	27	28	28

Abbreviation: W = week.

^a Last injection during the Maintenance Period occurs on Week 66.

A participant will be considered compliant if he or she received $\geq 75\%$ of the expected number of injections in the respective treatment period while enrolled in the study. Descriptive statistics for

percent compliance will be summarized. Sub-intervals of interest, such as compliance between visits, may also be presented.

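### A negative urine pregnancy test is a condition of dosing at each dosing visit, but the Schedule of Activities has no test at 4 of the 8 Induction dosing visits (Weeks 2, 6, 10 and 14)

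*Protocol*

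**What the plan says.** Footnote e to the Clinical Laboratory Tests table (Protocol Appendix 2, Section 10.2) applies to women of childbearing potential and women with a history of tubal ligation. It says of the local urine test: "Result must be negative before dosing at each dosing visit".

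Section 8.2.4 refers the reader to Appendix 2 "for the list of clinical laboratory tests to be performed and the SoA (Section 1.3) for their timing and frequency". The pregnancy-test row of the Induction SoA (Section 1.3) has a serum test at Visit 1 and urine tests at Visits 2, 4, 6, 8 and 10. Visits 3, 5, 7 and 9 are blank. The comment on that row adds: "Urine pregnancy tests will be performed locally and not captured in eCRF".

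Table 1 (Section 6.1) lists injections in every arm at Baseline and at Weeks 2, 4, 6, 8, 10, 12 and 14. Section 4.1 has site staff give all of them in the clinic. SAP Appendix 5 (Section 6.5) agrees on where Induction dosing stops: "Last injection during the Induction Period occurs on Week 14".

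On unscheduled testing, Appendix 2 says: "Additional tests may be performed at any time during the study as determined necessary by the investigator or required by local regulations". The Maintenance SoA adds that, where the investigator or local rules require it, "additional pregnancy testing can occur during the study treatment period".

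**The concern.** Two instructions in the same protocol disagree. The footnote makes a negative result a precondition at each dosing visit. The SoA, to which Section 8.2.4 assigns timing and frequency, schedules no test at half of the Induction dosing visits. Section 8 makes adherence to the SoA mandatory and bars waivers, so a site can follow the SoA exactly and still breach the footnote.

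The check matters because Appendix 4 (Section 10.4) requires a participant who becomes pregnant to discontinue study intervention, and the pre-dose urine test is the protocol's own means of finding out. The exposure is in the Q2W arm. At Week 2 it receives its second 500 mg loading dose, and at Weeks 6, 10 and 14 a 250 mg dose. The Q4W and placebo arms receive placebo at all four visits (for Q4W at Week 2, Table 1 reads "Week 2: 2 placebo injections"). Because urine results are not entered in the eCRF, the sponsor could not tell from the database which rule a site had followed.

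**Working it through.** The plan states no figure on this point, so the check is a comparison of schedules followed by a count.

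**Inputs**
- Dosing weeks: Protocol Table 1, cross-checked against the compliance table in SAP Appendix 5. The SAP table gives 2 + 2 + 1 + 1 + 1 + 1 + 1 + 1 = 10 injections from Week 0 to Week 14, which matches its stated total of 10.
- Test weeks: pregnancy-test rows of the Induction and Maintenance SoA. The Induction row fits the visit header on its page, and the hematology and chemistry row there alternates in the same way, so the blanks are real.
- Arm sizes: Section 9.2 (120 Q2W, 280 in total).
- Share of women of childbearing potential: not in the documents; assumed 30% to 50%.

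**Induction dosing visits against scheduled urine tests**

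| Visit | Week | Injection in every arm | Urine test in SoA |
|---|---|---|---|
| 2 | 0 | yes | yes |
| 3 | 2 | yes | no |
| 4 | 4 | yes | yes |
| 5 | 6 | yes | no |
| 6 | 8 | yes | yes |
| 7 | 10 | yes | no |
| 8 | 12 | yes | yes |
| 9 | 14 | yes | no |

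Without a test: 4 of 8 = 50%. If the Week 16 dose is counted (Visit 10, tested, and the first Maintenance dose): 4 of 9 = 44%.

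**All clinic visits from Visit 2 to Visit 24**
- Visits: 24 − 2 + 1 = 23.
- With a urine test: 5 (Visits 2, 4, 6, 8, 10) + 14 (Visits 11 to 24) = 19.
- Without: 23 − 19 = 4, all of them in Induction.

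**Lebrikizumab dosing occasions without the required result (Q2W arm, no dropout)**
- 30%: 120 × 0.30 × 4 = 36 × 4 = 144.
- 50%: 120 × 0.50 × 4 = 60 × 4 = 240.

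**Tests added if the SoA is changed in all arms**
- 30%: 280 × 0.30 × 4 = 84 × 4 = 336.
- 50%: 280 × 0.50 × 4 = 140 × 4 = 560.

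**The case against.** The best answer is that 4-weekly testing was intended and the footnote is merely too broad. From Week 20 onward, doses continue every 2 weeks while clinic visits and urine tests fall every 4 weeks, so the 12 home doses at Weeks 22, 26 and so on to 66 have no scheduled test. Induction testing at Weeks 0, 4, 8, 12 and 16 keeps the same interval. On this view the 19-of-23 count proves little, because most of the 19 are visits spaced 4 weeks apart.

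Much of this is fair. The visit count does not show that 2-weekly testing was meant, and the sponsor may well settle on rewording the footnote. It does not remove the conflict. Home doses between visits are not dosing visits, so the footnote does not reach them, whereas the four Induction visits are clinic dosing visits on any reading. The 4-weekly pattern is also broken at Week 18, which has a test two weeks after the one at Week 16 and is a dosing visit: "At Visit 11, participants or their caregiver will administer study intervention under site personnel supervision".

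It can also be said that a site reading the whole protocol would add the tests, since Appendix 2 names the SoA, Section 8.3.5 and its own table together as describing pregnancy testing and allows extra tests. But it gives no order of precedence, Section 8.3.5 contains no test schedule, and the extra tests are optional where the footnote is mandatory.

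Finally, the practical risk is limited. Inclusion criterion 7 requires contraception or abstinence, there is a serum test at screening, and the next scheduled urine test comes nominally two weeks after each blank visit. That stands, and it is why the point is minor.

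**Conclusion.** The inconsistency is real: 4 of 8 Induction dosing visits (50%) have no scheduled test although footnote e makes a negative result a condition of dosing there. That count rests on the documents alone.

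The estimate of 144 to 240 active dosing occasions depends on the assumed 30% to 50% share and ignores dropout. It leaves out women with a history of tubal ligation, whom the footnote also covers, and it counts doses, not pregnancies or harm. The matter is operational and concerns safety; no statistical quantity changes.

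**What to change.** Add a urine test at Visits 3, 5, 7 and 9 in the pregnancy-test row of the Induction SoA, in all arms so that the blind is kept. Coverage of Induction dosing visits then rises from 4 of 8 to 8 of 8. The cost is up to 4 local urine tests per affected woman, about 336 to 560 tests in all on the same assumption. The test is already in the protocol and the visits are already held in the clinic, so no visit is added.

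If the sponsor's medical team intends 4-weekly testing in Induction, reword footnote e so that a negative result is needed before dosing at visits where the SoA schedules a test. That costs one sentence and adds no tests. Neither option alters the analysis.

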#### **Hypersensitivity Testsa**

Anti-LY antibodies (immunogenicity)	Tryptase c
Anti-PLBL2 antibodies	
LY concentration (PK)	N-methylhistamine
Drug-Specific IgE b	Complements 
 
o C3, C3a, and C5a
 

Basophil activation test b	Cytokine panel 
 
o IL-6, IL-1<math>\beta</math>, IL-10 (or any cytokine panel that includes these 3 cytokines)
 

Abbreviations: IgE = immunoglobulin E; IL = interleukin; LY = LY3650150; NMH = N-methylhistamine; PK = pharmacokinetic; PLBL2 = phospholipase B-like 2

a Assayed by Lilly-designated laboratory. Results will not be provided to the investigative sites.

b Will be performed if a validated assay is available.

c If a tryptase sample is obtained more than 2 hours after the event (that is, within 2-12 hours) or is not obtained because more than 12 hours have lapsed since the event, obtain urine for NMH testing. Note that for tryptase serum samples obtained within 2-12 hours of the event, urine NMH testing is performed in addition to tryptase testing. Collect the first void urine following the event. Obtain a follow-up urine sample for NMH testing at the next regularly scheduled visit or after 4 weeks, whichever is later.

## 10.3. Appendix 3: Adverse Events: Definitions and Procedures for Recording, Evaluating, Follow-Up, and Reporting

### 10.3.1. Definition of AE

#### AE Definition

- An AE is any untoward medical occurrence in a patient or clinical study participant, temporally associated with the use of study intervention, whether or not considered related to the study intervention.
- NOTE: An AE can therefore be any unfavorable and unintended sign (including an abnormal laboratory finding), symptom, or disease (new or exacerbated) temporally associated with the use of study intervention.

